9.4 STATISTICAL ANALYSES

The SAP will be finalized prior to database lock and will include a more technical and detailed description of the statistical analyses described in this section. This section is a summary of the planned statistical analyses of the most important endpoints including primary and the key secondary endpoints.

9.4.1 Efficacy analyses

Statistical analysis methods for the primary, secondary, and tertiary/exploratory endpoints are presented in the table below ([Table 7](#)). In addition, for the primary and secondary endpoints, the primary estimand and details about the intercurrent events strategy and missing data handling are presented in Appendix 13 ([Section 10.13](#)).

Table 7 - Efficacy analyses

Endpoint	Statistical analysis methods
Primary	
Primary endpoint: Proportion of participants with negative ice cube provocation test at Week 24	
The primary efficacy endpoint will be analyzed using the Cochran-Mantel-Haenszel test stratified by region and background H1-antihistamine regular/daily use (Yes/No). The comparison of the proportions of participants with negative ice cube provocation test at Week 24 between dupilumab and placebo will be derived and the corresponding odd ratios and the 95% confidence interval (CI) will be reported. Participants who receive highly influential prohibited medications and/or highly influential rescue medications (details of selection will be specified in the statistical analysis plan [SAP]) will be considered as having positive ice cube provocation tests for time points after the medication usage. For other participants, all available data including those collected during the off-treatment period will be used to determine the positive/negative ice cube provocation test outcome. Participants with missing ice cube provocation test data at Week 24 will be considered as having positive ice cube provocation tests.
 
Sensitivity analysis
 
Tipping point analyses and other sensitivity analyses will be performed to confirm robustness of the results with respect to the missing data handling. Details of the sensitivity analyses will be provided in the SAP.
 
Subgroup analysis
 
To assess the consistency in treatment effects across different subgroup levels, subgroup analyses will be performed for the primary efficacy endpoint with respect to age group, gender, region, and other factors that will be specified in the SAP.

Secondary	

 Change from baseline in local wheal intensity at the provocation site at Week 12 and Week 24 using the wheal intensity Likert scale ranging from 0 to 5 (clinician evaluation) Change from baseline in local itch severity at the provocation site at Week 12 and Week 24 using the Peak Pruritus Numerical Rating Scale (NRS, score 0 to 10) (patient reported) Change from baseline in local skin burning sensation at the provocation site at Week 12 and Week 24 using the peak burning sensation NRS (patient reported) Change from baseline in local pain severity at the provocation site at Week 12 and Week 24 using the peak pain sensation NRS (patient reported) Change from baseline in urticaria control test (UCT 4-item) at Week 24 	
The secondary endpoints at Week 24 will be analyzed using analysis of covariance (ANCOVA) with multiple imputation. For participants taking highly influential prohibited medications and/or highly influential rescue medications (details of selection will be specified in the SAP), their data after the medication usage will be set to missing, and the WOCF approach (worst postbaseline observation for the participant will be carried forward) will be used to impute missing Week 24 value (for participants whose postbaseline values are all missing, the participant's baseline value will be used to impute the missing endpoint value). Participants who discontinue the treatment prematurely are encouraged to follow the planned clinical visits. For participants who did not take the highly influential prohibited medications and/or highly influential rescue medications, all data collected after treatment discontinuation will be used in the analysis. For these participants, missing data may still happen despite all efforts have been tried to collect the data after treatment discontinuation. For participants who discontinue study intervention due to lack of efficacy, all data collected after discontinuation will be used in the analysis, and a WOCF approach will be used to impute missing Week 24 value if needed. For participants who discontinue study intervention not due to lack of efficacy, a multiple imputation approach will be used to impute missing Week 24 value, and this multiple imputation will use all

Endpoint	Statistical analysis methods

Change from baseline in cold urticaria signs and symptoms severity at Week 24 on cold exposure days as measured by ColdUASChange from baseline in the proportion of cold urticaria sign and symptom free days at Week 24 on cold exposure days as measured by ColdUASChange from baseline in health-related quality of life (HRQoL) as measured by Dermatology Life Quality Index (DLQI) in participants ≥ 16 years old, and in Children's Dermatology Life Quality Index (CDLQI) in participants ≥ 12 to < 16 years old at Week 24Change from baseline in Cold Urticaria Quality of Life (ColdU-QoL) at Week 24.	
participants excluding participants who have taken the highly influential prohibited medications and/or highly influential rescue medications on or before Week 24 and excluding patients who discontinue due to lack of efficacy on or before Week 24. Each of the imputed complete data will be analyzed by fitting an analysis of covariance model with the baseline value of the endpoint, treatment group, region (combined countries), and background H1-antihistamine regular/daily use (Yes/No) as covariates.
 
Statistical inference obtained from all imputed data will be combined using Rubin's rule. Descriptive statistics including number of participants, mean, standard error, and least squares (LS) mean changes (and standard error) score will be provided.
 
In addition, difference of the dupilumab group against placebo in LS means and the corresponding 95% CI will be provided along with the p-values.
 
The continuous endpoints at Week 12 will be analyzed in a similar way as the secondary endpoints at Week 24.
 
Detailed analyses will be described in the SAP finalized before database lock.

Secondary 
Proportion of participants with negative ice cube provocation test at Week 12Proportion of well-controlled participants ($UCT \geq 12$) at Week 24Proportion of participants with an improvement of ≥ 3 in UCT 4- item from baseline to Week 24	These binary endpoints will be analyzed in a similar way as the primary endpoint.
Secondary 
Proportion of participants receiving rescue therapy for chronic induced ColdU during the planned treatment periodProportion of participants with cold exposure triggered urticaria requiring emergency medical care visit or treatment with epinephrine (at provocation test and/or at home)	These binary endpoints will be summarized using the count and percentage of participants.
Tertiary/Exploratory 
• [REDACTED]• [REDACTED]• [REDACTED]	

Endpoint	Statistical analysis methods
•	
•	
•	

A multiplicity hierarchical testing will be proposed to control the overall Type-I error rate for testing the primary endpoint, selected PRO(s), and the other key secondary endpoints. The study is considered positive when the primary endpoint achieves statistical significance. A detailed multiplicity adjustment procedure for the efficacy endpoints will be described in the study SAP.

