Participants will be randomized in a 1:1 ratio to dupilumab or placebo. The randomization will be first stratified by age (adults versus adolescents) with at least 4 adolescents. Then in adult's randomization will be stratified further by country and background H1-antihistamine regular/daily use (Yes/No). Randomization will not be stratified further in adolescents.

Number of participants using H1-antihistamine as needed prior to study entry should be at least █.

- **Analysis population**

The primary analysis population for the efficacy endpoints will be the randomized intent-to-treat population which includes all participants who have been allocated to a randomized treatment regardless of whether the treatment kit was used or not. The efficacy analyses will be conducted according to the treatment to which they were randomized.

The analysis population for safety endpoints is defined as all randomized participants exposed to study medication, regardless of the amount of treatment administered. The safety analyses will be conducted according to the treatment participants actually received.

- **Primary analysis**

The primary efficacy endpoint is the proportion of participants with negative ice cube provocation test at Week 24. The statistical hypothesis for comparing dupilumab against placebo on the primary endpoint is:

- Null hypothesis H0: No treatment difference between dupilumab and placebo.
- Alternative hypothesis H1: There is a treatment difference between dupilumab and placebo.

The primary efficacy endpoint will be analyzed using the Cochran-Mantel-Haenszel test stratified by region and background H1-antihistamine regular/daily use (Yes/No). The comparison of the proportions of participants with negative ice cube provocation test at Week 24 between dupilumab and placebo will be derived, and the corresponding odd ratios and the 95% confidence interval (CI) will be reported. Participants who receive highly influential prohibited medications and/or highly influential rescue medications (details of selection will be specified in the statistical analysis plan [SAP]) will be considered as having positive ice cube provocation tests for time points after the

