6.3 MEASURES TO MINIMIZE BIAS: RANDOMIZATION AND BLINDING

All participants will be centrally assigned to randomized IMP using an interactive response technology (IRT). The Investigator will be questioned during the interactive voice response system (IVRS) phone call/interactive web response system (IWRS) web module if he/she wishes to enroll the participant in the study. Before the study is initiated, the telephone number and call-in directions for the IVRS and/or the log in information and directions for the IWRS will be provided to each site.

At the screening visit (Visit 1), the Investigator or designee will contact the IRT system to receive the participant number. If a participant who had previously failed screening is approached for rescreening, a new ICF must be signed. In such case, a new participant number will be assigned by IRT.

Methods of assigning participants to treatment group

The randomized intervention kit number list is generated centrally by Sanofi and IMPs (dupilumab 300 mg, dupilumab 200 mg, or their matching placebo) are packaged in accordance with this list. The randomization and intervention allocation are performed centrally by an IRT. The IRT generates the participant randomization list and allocates the intervention number and the corresponding intervention kits to the participants according to it.

Participants will be randomized in a 1:1 ratio treatment arm as described in the [Table 3](#).

Randomization will be stratified by age (adolescent versus adult) and within adult group by country and background H1-antihistamine regular/daily use (Yes/No) (see [Section 6.1.2](#) for additional background therapy details).

Number of participants using H1-antihistamine as needed prior to study entry should be at least █. At screening (Visit 1), the Investigator or designee will contact the IRT system to receive the participant number. If a participant who had previously failed screening is approached for re-screening, a new ICF must be signed. In such case, a new participant number will be assigned by IRT.

A randomized participant is defined as a participant who has been allocated to a randomized intervention regardless of whether the treatment was administered or not (ie. participant registered by the IRT). A participant cannot be randomized more than once in the study.

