9.2 SAMPLE SIZE DETERMINATION

To adequately power the study for the comparison of the primary endpoint of the proportion of participants with negative ice cube provocation test at Week 24 between the 2 groups, the sample size was calculated based on the following assumptions:

1. The placebo group has █ of participants with negative ice cube provocation test at Week 24 and the dupilumab group has █ of participants with negative ice cube provocation test at Week 24.
2. There is a drop-out rate of 10% in both groups.
3. The statistical test is a Z test that is based on the difference of the 2 proportions with unpooled variance estimate and 2-sided 1% significance level.
4. Participants are equally randomized to the dupilumab group and the placebo group.

With these assumptions, 39 participants per group (78 participants in total) will provide 90% power to detect the difference of █ response rate in the dupilumab group and █ response rate in the placebo group. The sample size calculations were performed using nQuery+nTerim 4.0.

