4.4.1.2 Main analytical approach

The intercurrent event handling strategy for the key secondary endpoints is the treatment policy/composite approach.

This key secondary endpoints will be analyzed using an analysis of covariance (ANCOVA) model with baseline value of the endpoint, treatment group, region (combined countries), and background H1-antihistamine regular/daily use (Yes/No) as covariates, with intercurrent events and missing data being handled by a hybrid method of the worst-observation carried forward (WOCF) and multiple imputation. For participants who took highly influential prohibited medications and/or highly influential rescue medications (see [Table 4](#)), their data after the medication usage will be set to missing, and worst post-baseline value on or before the time of the medication usage will be used to impute missing Week 24 value (for participants whose post-baseline values are all missing, the baseline will be used to impute). Participants who discontinue the treatment prematurely are encouraged to follow the planned clinical visits. For participants who did not take the highly influential prohibited medications and/or highly influential rescue medications, all data collected after treatment discontinuation will be used in the analysis. For participants who discontinue study intervention due to lack of efficacy, all data collected after discontinuation will be used in the analysis, and a WOCF approach will be used to impute missing Week 24 value if needed (i.e., due to study discontinuation). For participants who discontinue study intervention not due to lack of efficacy, all data collected after discontinuation will be used in the analysis, and a multiple imputation approach will be used to impute missing Week 24 value if needed (i.e., due to study discontinuation). This multiple imputation will use all participants excluding participants who have taken the highly influential prohibited medications and/or highly influential rescue medications on or before Week 24 and excluding participants who discontinue due to lack of efficacy on or before Week 24. Each of the imputed complete data will be analyzed by fitting an analysis of covariance model as described above. Statistical inference obtained from all imputed data will be combined using Rubin's rule. Descriptive statistics including number of participants, mean, standard error, and least squares (LS) mean changes (and standard error) score will be provided. In addition, difference of the dupilumab group against placebo in LS means and the corresponding 95% confidence intervals (CI) will be provided along with the p-values.

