4.6 MULTIPLICITY ISSUES

To strongly control the family-wise type-I error rate for testing the primary and selected secondary endpoints, hierarchical testing procedure is used. The overall two-sided alpha is 0.01. The comparisons with placebo will be tested based on the hierarchical order below at 2-sided $\alpha = 0.01$.

Order of the testing hierarchy:

1. Proportion of participants with negative ice cube provocation test at Week 24.
2. Change from baseline in local wheal intensity at the provocation site at Week 24 using the wheal intensity Likert scale ranging from 0 to 5 (clinician evaluation).
3. Change from baseline in proportion of cold urticaria symptom free days at Week 24 (exposure-adjusted and measured by ColdUAS).
4. Change from baseline in local itch severity at the provocation site at Week 24 using the Peak Pruritus Numerical Rating Scale (NRS, score 0 to 10) (patient reported).
5. Change from baseline in health-related quality-of-life (HRQoL) as measured by Dermatology Life Quality Index (DLQI) in participants ≥ 16 years old.

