5.3 APPENDIX 3 DEMOGRAPHICS AND BASELINE CHARACTERISTICS, PRIOR OR CONCOMITANT MEDICATIONS

Demographics, baseline characteristics, medical surgical history

The following demographics and baseline characteristics, medical and surgical history and disease characteristics at baseline will be summarized using descriptive statistics in the randomized population.

Demographic variables are

- Age in years (quantitative and qualitative variable: 12-<18, 18-<40, 40-<65, 65-<75 and ≥ 75 years),
- Gender (Male, Female),
- Race (White, Black or African American, Asian, American Indian or Alaska Native, Native Hawaiian or other Pacific Island, unknown),
- Ethnicity (Hispanic or Latino, Not Hispanic or Latino, Unknown)
- Region (**Asia**: Japan; **Latin America**: Argentina; **Western Countries**: Canada, USA, Germany)
- Weight in kg (quantitative and qualitative variable: <60, ≥ 60 kg)
- BMI in kg/m² (quantitative and qualitative variable: <30, ≥ 30 kg/m²)

Baseline safety and efficacy parameters (apart from those listed above) will be presented along with the safety and efficacy summaries.

Medical (or surgical) history includes all the relevant medical (or surgical) history during the lifetime of the participant.

This information will be coded using the version of MedDRA currently in effect at Sanofi at the time of database lock.

Comorbidity will be summarized separately. The following comorbid diseases will be summarized from electronic case report form (eCRF) pages which were filled in by investigators based on participant reporting. Angioedema history will be further summarized under disease characteristics at baseline.

CSU (Yes, Ongoing condition)

Atopic Dermatitis (Yes, Ongoing condition)

Allergic rhinitis (Yes, Ongoing condition)

Allergic Conjunctivitis (Yes, Ongoing condition)

Asthma (Yes, Ongoing condition)

Food allergy (Yes, Ongoing condition)

Chronic Rhinosinusitis (Yes, Ongoing condition)

Nasal Polyps (Yes, Ongoing condition)

Eosinophilic Esophagitis (Yes, Ongoing condition)

Disease characteristics at baseline

The following baseline disease characteristics will be summarized by intervention group:

- Age at onset of cold urticaria (years)
- Duration of cold urticaria before screening visit (years) to be derived as
- (Year of screening visit – Year of first diagnosis of cold urticaria) + (month of screening visit-month of first diagnosis of cold urticaria)/12

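### Adults are randomised within country, but the ANCOVA for hierarchy endpoints 2 to 5 adjusts only for region, which merges Canada, the USA and Germany; the test is valid but may be slightly conservative

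*Protocol*

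**What the plan says.** **Randomisation.** Protocol Section 6.3: "Randomization will be stratified by age (adolescent versus adult) and within adult group by country and background H1-antihistamine regular/daily use (Yes/No". The synopsis adds "Randomization will not be stratified further in adolescents"; at least 4 adolescents are planned.

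**Model.** Protocol Table 7 gives an ANCOVA with the baseline value, "treatment group, region (combined countries), and background H1-antihistamine regular/daily use (Yes/No) as covariates". SAP Section 4.4.1.2 agrees: "baseline value of the endpoint, treatment group, region (combined countries), and background H1-antihistamine regular/daily use (Yes/No) as covariates". SAP Section 4.4.2 carries the same procedure over to the supportive change-from-baseline endpoints, including itch NRS and DLQI.

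**Region.** SAP Section 5.3 defines three regions: Asia (Japan only), Latin America (Argentina only) and Western Countries ("Canada, USA, Germany").

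**Testing.** SAP Section 4.6: "The overall two-sided alpha is 0.01". Step 1 is the primary endpoint. Steps 2 to 5 are wheal intensity, symptom-free days, itch NRS and DLQI, all changes from baseline at Week 24.

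**Power.** Protocol Section 9.2 says "39 participants per group (78 participants in total) will provide 90% power to detect the difference of" two response rates, which are blacked out. This covers the primary endpoint only. For steps 2 to 5 the documents give no effect size, SD, between-country variation or power. They plan no analysis adjusted for country.

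**The concern.** Because Japan and Argentina are each a region by themselves, using region instead of country has one effect: it drops the distinction between Canada, the USA and Germany. For adults, the randomisation controls balance on that distinction. When arms are balanced on a factor that predicts outcome and the model omits it, the factor's variation stays in the residual. The estimated standard error is then larger than the true one, and the test rejects less often than it could.

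Country differences are plausible. Wheal intensity is rated by local investigators, the NRS scores are patient reports, and the ColdUAS endpoint depends on cold exposure in daily life.

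The hierarchy is a fixed sequence at 1% with about 39 participants per arm, so a miss at step 2 ends confirmatory testing of steps 3 to 5. Even a small avoidable loss is worth removing if removal costs almost nothing.

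**Working it through.** **1. The plan's own figure.** The response rates are blacked out, so 90% power cannot be reproduced exactly, but it is coherent. With 10% drop-out, 35 evaluable per arm gives 35/0.9 = 38.9, rounded up to 39. One pair that fits is 10% v 48%: SE = √[(0.10×0.90 + 0.48×0.52)/35] = 0.0985; 0.38/0.0985 − 2.576 = 1.28; power 90%. Nothing here bears on steps 2 to 5.

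**2. Size of the model change.** Region has 3 levels (2 terms) and country has 5 (4 terms). With 78 participants the region model leaves 78 − (intercept 1 + treatment 1 + baseline 1 + region 2 + antihistamine 1) = 72 residual degrees of freedom. The country model leaves 70.

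**3. Assumptions for power.** None of these is in the documents: country shares, randomisation blocks of 4, effect size, baseline correlation, between-country spread, complete data and normal residuals.

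**4. Power, country shifting Week 24 only.** 12,000 simulated trials per setting; effect 0.8 SD; baseline–outcome correlation 0.4; 60% regular antihistamine use; 4 adolescents in their own stratum. Shares for Germany/USA/Canada/Japan/Argentina were 35/20/10/20/15% (mix A) and 25/25/15/20/15% (mix B).

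| Between-country SD | Mix A, region → country | Mix B, region → country |
|---|---|---|
| 0 | 87.7 → 87.6% (−0.1) | 88.1 → 87.8% (−0.3) |
| 0.3 | 86.4 → 87.2% (+0.8) | 86.7 → 87.8% (+1.1) |
| 0.5 | 84.5 → 88.0% (+3.5) | 83.1 → 87.0% (+3.9) |

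**5. A second parameterisation.** 8,000 trials per cell, with country's share of the residual variance (net of baseline) set directly and d = 0.79. Read across each row, not down.

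| Country share of variance | Equal countries | Western-heavy |
|---|---|---|
| 0 | 79.2 → 78.9% | 78.5 → 78.5% |
| 0.02 | 79.2 → 79.2% | 79.1 → 79.5% |
| 0.05 | 80.0 → 80.5% | 80.2 → 81.0% |
| 0.10 | 82.6 → 84.0% | 81.6 → 83.4% |
| 0.20 | 84.8 → 87.8% | 84.4 → 87.7% |

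With d = 0.89 the change runs from −0.4 points (share 0) to about +2 points (share 0.20). Monte Carlo error is about 0.45 points on each power figure, and less on the paired differences.

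**6. Country shifting baseline and Week 24 alike.** Baseline is already a covariate. With a slope of about 0.4, a shift c at both visits leaves about (1 − 0.4)c after adjustment, so an SD of 0.5 acts like 0.6 × 0.5 = 0.30 and an SD of 0.3 like 0.18. The gain at SD 0.5 should therefore resemble the SD 0.3 row in step 4. Rerunning the step 4 setting with the shift at both visits gave gains of −0.1 to +0.1 points at SD 0.3 and 1.1 to 1.2 at SD 0.5. A separate run gave 0.1 to 0.9 across the two SDs.

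**7. Size of the test.** At variance share 0.20 the region model rejects a true null 0.66% (equal) and 0.76% (Western-heavy) of the time, against a nominal 1%; the country model gives 1.06% and 0.86%. The Monte Carlo error is √(0.01×0.99/8,000) = 0.11%. At share 0.05 and below, all region-model values lie between 0.81% and 1.09%. The planned test therefore does not inflate type I error, and it is clearly conservative only when the country spread is large.

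**The case against.** **No error or contradiction.** The protocol and SAP agree on the model, the primary CMH test also uses region, and pooling countries in a trial of 78 is a defensible prespecified choice. This stands: the point concerns efficiency only.

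**The sources of variation are already limited.** Protocol Section 3.1 standardises the ice cube test through an operational manual, Section 8.1.1 recommends the same reader throughout for each participant, and the ColdUAS endpoint counts only cold-exposure days. This largely stands for wheal intensity. A stable reader style shifts both visits, which is the case with a gain of about 0 to 1 point. It stands less well for symptom-free days, whose baseline window (days −14 to −1) and Week 24 window (days 156 to 169) fall in different seasons. Country differences in one season need not match those in the other.

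**Stronger readings.** A reader might infer that the 1% tests do lose power, by up to 4 points. The documents do not support this: they give no between-country variation, and the largest figure needs both a large spread and a shift absent at baseline. A reader might also infer that leaving out a randomisation factor makes the tests invalid. It does not; any departure from the nominal 1% is toward conservatism.

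**Other factors.** The age stratum is also missing from the model. That is true, but the planned minimum is 4 adolescents of 78, and they are not stratified by country, so the balance argument applies to adults.

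**Conclusion.** The mismatch between randomisation and model is as described, and the planned analysis is valid. Whether it loses power depends on whether Week 24 outcomes differ between Canada, the USA and Germany after baseline adjustment, which the documents do not address. Under the assumptions listed, changing from region to country:

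- costs about 0.4 points or less if country has no effect;
- gains about 0 to 1 point if country shifts baseline and Week 24 alike;
- gains about 1 to 4 points if it shifts Week 24 only, with between-country SD 0.3 to 0.5.

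The possible gain outweighs the possible cost, but both are small. This is a free or cheap improvement of minor importance, not a defect in the confirmatory tests.

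**What to change.** In protocol Table 7 and SAP Section 4.4.1.2 (and so 4.4.2 by reference), replace region by country in the ANCOVA. The same covariate list appears in the protocol synopsis, protocol Table 11 and SAP Table 2, and should be changed to match.

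State one fixed rule before unblinding: if Canada, the USA or Germany has fewer than 4 participants, merge it with the next smallest of these three. Japan and Argentina stay as they are, since each is the only country in its region and has no natural partner.

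Keep region for the primary CMH test. There the trade-off is less one-sided. Country would raise the strata from 3×2 = 6 to 5×2 = 10, or from 13 to 7.8 participants per stratum on average. In 6,000 simulated trials (10% v 46% response), power went from 86.0% to 85.2% with no country effect, and from 78.8% to 80.6% with a between-country SD of 1.0 on the logit scale.

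The cost is SAP and protocol wording, one model term and two degrees of freedom (72 to 70). If the sponsor prefers region, a sentence justifying the pooling and a country-adjusted sensitivity analysis would be the minimum.
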